#### **Patient re-registration steps:**

- Log into the OPEN registration system and select the appropriate patient.
- Select the next registration step.
- Complete OPEN Enrollment Form for the patient to be registered to the open-label arm.
- Enter Cycle # of the last treatment received during blinded treatment, as well as the stratification factors, on the OPEN Enrollment Form.
- Once the open-label registration has been successfully completed confirmation will be displayed in OPEN.

If assistance is needed with this process, contact the Alliance Registration Office.

Following re-registration, open-label metformin should be ordered per Section 15.1.8.

#### 7.0 PROTOCOL TREATMENT

#### 7.1 Treatment Schedule

#### 7.1.1 Months 1-12

| Agent     | Dose and Duration  |  |
|-----------|--|--|
|           | 850 mg (1 tablet) p.o. one a day for 4 weeks (ramp-up period),         |  |
| Metformin | then   |  |
| /Placebo  | 850 mg (1 tablet) p.o. twice a day, (pending gastrointestinal toxicity |  |
|           | evaluation) for months 2-12.   |  |

#### 7.1.2 Months 13-24 (See Section 7.3)

| For unblinded patients originally randomized to metformin: |  |  |  |
|--|--|--|--|
| Agent Dose and Duration                                    |  |  |  |
| Metformin  | 850mg (1 tablet) p.o. twice a day for months 13-24 |  |  |

| For unblinded patients originally randomized to placebo who choose to crossover to metformin: |   |  |  |
|---|---|--|--|
| Agent   | Agent Dose and Duration   |  |  |
|   | 850 mg (1 tablet) p.o. one a day for 4 weeks (ramp-up period), then   |  |  |
| Metformin   | tformin
850 mg (1 tablet) p.o. twice a day, (pending gastrointestinal toxicity
evaluation) for months 2-12. |  |  |

| For unblinded patients originally randomized to placebo who choose not to |  |  |
|--|--|--|
| crossover to metformin:  |  |  |
| Agent Dose and Duration  |  |  |

| Agent | Dose and Duration |  |
|-------|-------------------|--|
| None  | Months 13-24      |  |

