#### 6.9 Open-label and crossover re-registration (step 2) procedures

At the time of the 12-month RPFNA visit, all patients will be unblinded per Section 7.3.

All patients who were randomized to receive metformin will be re-registered and begin receiving open-label metformin as described below.

Patients who were randomized to receive placebo and elect to cross over to open-label metformin therapy will be re-registered to receive open-label metformin as follows:

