#### 7.4 Emergency unblinding

Before the crossover at 12 months, unblinding may be done only in cases of an emergency. Follow the directions below to unblind patient treatment. Please note that if a treatment assignment is unblinded, the patient must discontinue protocol therapy.

Emergency Unblinding Procedures:

Examples of emergencies include 1) a life-threatening unexpected adverse event that is at least possibly related to the investigational agent and for which unblinding would influence treatment decisions; or 2) medication error, such as accidental overdose. Expected adverse events are listed in the "Toxicities" section below.

Contact the Alliance Executive Officer on call by calling

The institution must provide the following information to the Alliance Executive Officer:

- Alliance study ID ("A211102")
- Alliance patient ID number (e.g., "999999")
- Patient initials (e.g., "L,FM")
- Institution name
- Name and telephone number of treating physician
- Name and contact information of person requesting the unblinding procedure
- Name and contact information of person to inform of treatment assignment
- Reason for emergency unblinding

Please remember that emergency unblinding request may be authorized only by an Alliance Executive Officer, and emergency unblinding applies only if unblinding would influence management of the medical situation.

After the Executive Officer deems unblinding is warranted, the treatment assignment will be provided to the contact person at the treating site.

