|  | Vomiting                 |           | then resume study treatment as follows:       |  |  |  |  |  |  |
|  | disorders Other          |           | remp up schedule (one tablet per day for 4    |  |  |  |  |  |  |
|  | specify                  |           | weeks then one tablet twice a day if          |  |  |  |  |  |  |
|  | speeny                   |           | tolerated) If toxicity persists or recurs the |  |  |  |  |  |  |
|  |                          |           | study drug should be adjusted to the          |  |  |  |  |  |  |
|  |                          |           | maximum dose that is tolerated with Grade     |  |  |  |  |  |  |
|  |                          |           | 1 toxicity or lower. A second attempt to      |  |  |  |  |  |  |
|  |                          |           | increase to full dose should be made 3        |  |  |  |  |  |  |
|  |                          |           | months later and if the full dose is not      |  |  |  |  |  |  |
|  |                          |           | tolerated at that time, the maximum           |  |  |  |  |  |  |
|  |                          |           | tolerated dose should be used for the         |  |  |  |  |  |  |
|  |                          |           | remainder of the 2-year (metformin group)     |  |  |  |  |  |  |
|  |                          |           | or 1-year (Placebo crossover group)           |  |  |  |  |  |  |
|  |                          |           | intervention.                                 |  |  |  |  |  |  |

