#### 13.3 Pregnancy

If a patient should become pregnant, the study medication will be discontinued and the patient should still be followed per the test schedule for data collection time points. The Off Treatment Form must be submitted per the schedule of forms.

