Open-label metformin: All patients will be unblinded at 12 months (see Section 6.9). All patients, except those who were randomized to placebo and who opt not to cross over to open-label metformin will receive open-label metformin. After re-registering the patient per Section 6.9, site staff will order patient-specific supplies of open-label metformin using the A211102 Drug Order Form. Orders should be placed at least 1 week prior to the patients' 12-, 15-, 18-, and 21-month visits.

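### Sections 6.9 and 15.1.8 send every woman randomized to metformin to open-label drug at month 12, which conflicts with the rules that stop study drug during year 1

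*Combined protocol and SAP*

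**What the plan says.** Three places say what the metformin arm receives after month 12.

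- Section 6.9, on Step 2 re-registration: "All patients who were randomized to receive metformin will be re-registered and begin receiving open-label metformin as described below".
- Section 15.1.8, in the open-label paragraph: "All patients, except those who were randomized to placebo and who opt not to cross over to open-label metformin will receive open-label metformin".
- Section 7.1.2, in the row headed "For unblinded patients originally randomized to metformin", gives the dose as "850mg (1 tablet) p.o. twice a day for months 13-24".

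None of the three depends on whether the woman is still taking drug or on her current dose. Section 7.3.1 is worded differently: it re-registers patients who had been receiving metformin.

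Other sections take women off study drug. Section 8.2.1 discontinues it for grade 3 or 4 diarrhea. Section 7.4 says that "if a treatment assignment is unblinded, the patient must discontinue protocol therapy". Section 13.3 says: "If a patient should become pregnant, the study medication will be discontinued". Section 13.1 covers women who stop because of side effects, and 13.7 takes a woman off treatment if she is found to be on any of six listed drugs. Sections 13.1 and 13.3 both continue follow-up on the test schedule for data collection.

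Section 8.2.2 deals with dose. If a second attempt at full dose fails, the maximum "tolerated dose should be used for the" "remainder of the 2-year (metformin group"), or of the 1-year period for the placebo crossover group.

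**The concern.** Step 2 is defined by what a woman was randomized to, while the stopping rules depend on what happened to her in year 1. A woman randomized to metformin whose drug was stopped, and who is still being followed, satisfies both. Section 15.1.8 sharpens the problem: it lists an exception, and she is not in it.

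The stake is re-exposure. Site staff who follow 6.9 literally would re-register and supply a woman whose drug had been stopped for cause. There is a smaller statistical consequence. The 24-month metformin-arm summary would include women whose year-2 treatment the protocol describes in two ways, and nothing in the listed re-registration steps records which description was followed.

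**Working it through.** No calculation decides this, so the rules are set side by side for a woman randomized to metformin.

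| Situation in year 1 | Rule | Kept on the test schedule? | What the month-12 text says |
|---|---|---|---|
| Stopped for side effects, taken to include grade 3-4 diarrhea | 13.1, 8.2.1 | Yes, unless she refuses | 6.9 and 15.1.8: receives open-label metformin |
| Stopped for pregnancy | 13.3 | Yes | Same |
| Emergency unblinding | 7.4 | Not stated | Same, if she is still on study |
| Found on a listed drug | 13.7 | Not stated | Same, if she is still on study |
| Held at a maximum tolerated dose | 8.2.2 | On treatment | 7.1.2: twice daily. 8.2.2: maximum tolerated dose |

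**Stopped women.** The first two rows are the firm conflict, because the documents themselves keep these women on study to month 12. The third and fourth rows depend on whether the women stay in follow-up, which 7.4 and 13.7 do not say.

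**Does 7.3.1 settle it?** Two readings are possible. Section 7.3 also tells the CRA to call and find out which agent the patient is receiving, where the word means assignment. On that reading 7.3.1 is as broad as 6.9. If it instead means women still taking drug, it conflicts with 6.9 and 15.1.8. Either way the sections do not agree with the rest of the protocol.

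**Would re-registration catch it?** The steps in 6.9 ask for the cycle number of the last blinded treatment and the stratification factors. The cycle number may show indirectly that a woman stopped early, but no listed step asks for treatment status or current dose, or says what to do about either.

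**Dose row.** Twice daily is 2 x 850 = 1700 mg/day. A woman held at one tablet takes 850 mg/day. The months 1-12 row and the crossover row make twice-daily dosing conditional on a gastrointestinal toxicity evaluation. The metformin continuation row has no such condition and no reference to Section 8. Section 8.2 also says that, once individual tolerance is known, its modifications become guidelines.

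**Number affected.** Randomized per arm: 96 / 2 = 48. Section 16.1.1 bases power on 44 per arm at month 12. The 10% drop-out in that section and the withdrawal figure of at most 10% in 16.2.2.5 concern leaving the study. Neither is a rate of stopping or reducing drug while still followed, so no count can be derived.

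**Reach.** Section 16.2.1.1 places the primary comparison at month 12, ahead of the open-label year. Sections 2.1 and 11.1 mention month 24 alongside the primary objective, but 16.1.1 states that the 24-month outcomes are exploratory, and 16.2.2.1 plans only to summarize the metformin arm at that time.

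**The case against.** The strongest reply is that ordinary reading resolves most of this.

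- Section 7.1 is the treatment schedule and Section 8 modifies it for toxicity. Section 8.2.2 expressly runs through the 2-year metformin-group intervention, so it was written with year 2 in view. This stands. A reader might infer that 7.1.2 and 8.2.2 flatly contradict each other on dose. The documents do not support that; what remains is a missing cross-reference.
- The toxicity condition appears only in rows where a ramp-up leads to twice-daily dosing, so its absence from the continuation row may be natural. This is fair. The absence makes the text less clear but proves nothing alone.
- The heading of 7.1.2 and the text of 6.9 both point to 7.3, and 7.3.1 can be read as limited to women still on drug. This is a possible reading but not the only one, and it leaves 6.9 and 15.1.8 too broad.
- Women stopped under 13.1 and 13.3 are kept for data collection and have an Off Treatment Form, and nothing in 7.4 suggests its discontinuation is temporary. The month-12 footnote to the test schedule mentions only placebo crossover. Section 15.1.8 is a supply paragraph. These points make an actual restart less likely. They do not remove the conflict, because 6.9 is the re-registration procedure itself and states no exception for women already off drug.

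**Conclusion.** The point holds for women already off drug. The wording of 6.9 and 15.1.8 covers them, the stopping rules exclude them, and 13.1 and 13.3 bring some of them to month 12. The dose question is secondary: 7.1.2 and 8.2.2 need a stated relation to each other.

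Three further inferences go beyond the documents. First, that stopped women will in fact be restarted at full dose: a careful investigator may well avoid this, and the fault is only that the text does not ensure it. Second, that a particular number of women is affected: any such number would rest on an assumed rate. Third, that the 24-month data cannot be interpreted: they are exploratory, no dose-specific analysis of them is planned, and the limit is only that the summary may mix women treated under differing instructions.

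The conclusion assumes that grade 3-4 diarrhea counts as a side effect under 13.1. It takes no view on which clinical rule is right. The matter deserves correction because it concerns women whose drug was stopped or reduced for cause, and that does not depend on the count.

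**What to change.** Reconcile 6.9, 7.1.2, 7.3.1 and 15.1.8 with 7.4, 8.2 and Section 13. The revised text should do three things:

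1. State which women Step 2 covers, in the same words in 6.9, 7.3.1 and 15.1.8.
2. State what Step 2 means for women whose study drug was stopped before month 12.
3. State how the months 13-24 row of 7.1.2 relates to 8.2.2.

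The sponsor decides the clinical rule in each case. The cost is amendment wording in four sections, with no change to sample size or to the primary analysis.

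Optionally, add treatment status and current dose to the Step 2 enrollment form, which sites already complete at re-registration. The 24-month metformin-arm summary could then describe the exposure of re-registered women as they entered year 2.

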#### 7.2 Patient Monitoring

A Patient Medication Diary will be provided for each patient for the ramp-up period and telephone contact will be made with the patient one month +/- 3 days after enrollment to assess compliance, toxicity, and to ensure the patient has increased medication to twice daily. (The diary is intended only as a tool to assist subjects in adjusting to full dose at the correct time after starting study treatment.) A record of the telephone contact will be made on the Nurse/CRA Phone Contact Guide (see Appendix IV). Any problems identified will be communicated to the responsible Investigator.

Optimal medication compliance is defined as  $\geq 80\%$ . Patients found to be non-adherent with their medication will receive additional interventions by the treatment team to improve adherence (i.e., registered nurse phone calls as a first-line intervention and extra study visits will be scheduled if non-adherence is still noted at the next follow-up time point).

#### 7.3 Crossover

During the first 12 months of treatment, patients will not be unblinded except in cases of emergencies (see Section 7.5)

**Prior to the patient's 12 month clinic visit**, the CRA must call the Alliance Registration Office to find out which study agent the patient is receiving.

- 7.3.1 Patients who were receiving metformin will be re-registered to receive open-label metformin.
- 7.3.2 Patients who were receiving placebo are eligible to cross over to metformin therapy.

If the patient was receiving placebo, the CRA must contact her and ask her if she wishes to

- 1) receive metformin 850 p.o. bid for 12 mos. (including 4-week ramp-up of 850 mg p.o. qd) or
- 2) discontinue protocol therapy.

If the patient wishes to crossover to metformin therapy, the CRA will then re-register the patient per Section 6.9 and to receive open label metformin, and the patient will be administered the drug as outlined in Section 7.1.2.

**Patient Monitoring:** The Patient Medication Diary will be provided for each patient who crosses over from placebo to open-label metformin to be completed during the ramp-up period and telephone contact will be made with the patient one month +/- 3 days after crossover to assess compliance, toxicity, and to ensure the patient has increased medication to twice daily. (The diary is intended only as a tool to assist patients in adjusting to full dose at the correct time after starting study treatment.) A record of the telephone contact will be made on the Nurse/CRA Phone Contact Guide (see Appendix IV). Any problems identified will be communicated to the responsible Investigator.

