| Mandatory Research Blood
Draw (see Section 14.0) R          |   | $X^7$   |                              | X                                        |  |
| Patient-reported knowledge
of the arm to which they
were randomized |   |   |                              | X                                       |  |

\* The ramp-up period occurs during the first 4 weeks of blinded treatment and during the first 4 weeks of open-label treatment for patients who cross over from placebo to metformin.

\*\* Prior to the 12-month clinic visit, the CRA must call the Alliance Registration Office [contact]) to unblind the patient's treatment assignment. Patients who were receiving placebo are eligible to crossover to metformin treatment (see Section 6.8).

+/- 3 weeks for Month 6 visit; +/- 30 days for Month 12, 24, and 36 visits.

1. For women of childbearing potential only. Must be done  $\leq$ 7 days prior to registration/randomization.

2. Baseline mammogram must have been done within 365 days of pre-registration. Mammographic screening should be continued as part of the patient's regular medical care.

 See Section 14.0 for information regarding available RPFNA kits and RPFNA sample submission instructions. See Appendix II for RPFNA collection instructions. Following RPFNA, submit the RPFNA Procedure Documentation Form, available at the Alliance and CTSU A211102 study-specific web pages.

4. RPFNA at 12 months and 24 months ONLY. RPFNA at 24 months is optional for patients who were randomized to placebo and opted not to continue protocol treatment after 12 months.

5. At completion of 4 week ramp-up (phone).

6. The Patient Medication Diary will be provided for each patient for the ramp-up period. Telephone contact will be made with the patient at the end of the ramp up period to assess compliance and adverse events.

7. Blood collections (EDTA whole blood and serum samples) must be collected Monday-Thursday ONLY.

8. Pre-treatment RPFNA specimens must be submitted immediately following pre-registration (see Sections 6.6 and 14.0).

- 9. CRA or provider will make a follow-up phone call the day following the RPFNA to check in with the participant and review any side effects of the procedure (see Appendix V).

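### The arm is released to site staff before the month-12 RPFNA that supplies the primary endpoint, and placebo women may learn it before the arm-knowledge question

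*Combined protocol and SAP*

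**What the plan says.** The release of the arm is described in four places.

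- Section 4.0, footnote to the on-treatment visits: "Prior to the 12-month clinic visit, the CRA must call the Alliance Registration Office" to unblind the assignment. The window is plus or minus "30 days for Month 12, 24, and 36 visits".
- Section 7.3: ahead of the 12-month clinic visit, "the CRA must call the Alliance Registration Office to find out which study agent the patient is receiving". For the metformin arm, "Patients who were receiving metformin will be re-registered to receive open-label metformin", with no choice to make. For the placebo arm, "If the patient was receiving placebo, the CRA must contact her and ask her if she wishes to" take metformin or stop protocol therapy, and then "If the patient wishes to crossover to metformin therapy, the CRA will then re-register the patient per Section 6.9".
- Section 6.9: "At the time of the 12-month RPFNA visit, all patients will be unblinded per Section 7.3". The re-registration steps end with "Following re-registration, open-label metformin should be ordered per Section 15.1.8".
- Section 15.1.8: the open-label order follows re-registration and is due at least one week before the 12-month visit.

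Section 7.3 also opens by ruling out patient unblinding during the first 12 months except in emergencies. Footnote 10 of Section 4.0 and Section 16.2.2.5 require the single arm-knowledge question at month 12, before the patient is unblinded or crosses over. Section 16.2.2.5 uses the answer for sensitivity analyses that drop unblinded patients. The primary comparison (Section 16.2.1.1) is atypia at month 12. Section 16.1.1 makes the 24-month outcomes exploratory.

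**The concern.** A double-blind comparison should stay blind until its endpoint has been collected. Here the blind is lifted for site staff by routine procedure just before the sample that decides the trial. Under Appendix II the CRA, who is the person told the arm, helps with collection and expels and rinses each needle. Sampling is standardised but leaves some judgement: several passes are made per needle, and a needle is withdrawn once material shows in the hub. Knowledge of the arm could also affect the effort made to bring a woman back for an invasive aspirate, while Section 16.2.1.2 treats unsatisfactory repeats as missing at random.

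The second issue is the arm-knowledge question, added after one patient identified her tablets. If a placebo woman has already been offered crossover when she is asked, she can truthfully say that she knew. Her answer then mixes planned release with premature unblinding, and the sensitivity analysis could wrongly exclude her. Because Section 7.3 specifies the crossover contact only for placebo women, the error would fall on one arm. The question cannot detect staff knowledge at all.

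**Working it through.** **The plan's own figure.** The only stated number bearing on month 12 is 90% power for 90% versus 60% atypia with 44 per arm and alpha 5% (Section 16.2.1.1; two-sided assumed). Pooled proportion = 0.75. SE under the null = sqrt(2 × 0.75 × 0.25 / 44) = 0.0923. SE under the alternative = sqrt((0.9 × 0.1 + 0.6 × 0.4) / 44) = 0.0866. z = (0.30 − 1.96 × 0.0923) / 0.0866 = 1.37, so power is 91.5%. The stated figure reproduces and is not in dispute.

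**Order of steps, metformin woman.** CRA call (4.0, 7.3) → re-registration (7.3.1) → order at least 7 days before the visit (15.1.8) → visit with RPFNA (6.9). Staff know the arm at least 7 days before the aspirate. The patient need not be told until the visit, so 4.0, 6.9 and the opening of 7.3 can be reconciled for her.

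**Order of steps, placebo woman who crosses over.** CRA call → crossover offer and choice (7.3.2) → re-registration → order at least 7 days before the visit → visit with RPFNA. The offer discloses the arm. It must precede re-registration, and re-registration must precede the order, so she learns her arm at least 7 days before the visit. This is an inference, because 7.3.2 gives no contact date. Section 4.0 lists the arm-knowledge question among the on-treatment visit procedures, at month 12. Sections 6.9, 7.3 and 15.1.8 contain no step that places it before the offer.

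**Placebo woman who declines.** No drug is ordered, so the 7-day lead does not apply to her. The CRA call still precedes the visit, and the same 7.3.2 contact is needed to learn that she declines.

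**Dates** (12 months taken as 365 days):

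| Visit | Visit day | Order due by | Relative to day 365 |
|---|---|---|---|
| Earliest | 365 − 30 = 335 | 335 − 7 = 328 | 37 days before |
| Latest | 365 + 30 = 395 | 395 − 7 = 388 | 23 days after |

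For any visit up to day 372 the order is due by day 365 (372 − 7), so a woman crossing over learns her arm within the first 12 months.

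**Reach.** Section 16.1.1 plans 88 women at month 12, 44 per arm. Staff knowledge applies to all 88; inferred patient knowledge applies to at most 44.

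**Illustration only.** Suppose a share of placebo women answer yes because of the crossover contact and are excluded, with metformin kept at 44. The same formula with unequal arms gives the power of the sensitivity analysis. The documents give no such share.

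| Placebo women excluded | Placebo vs metformin | Power |
|---|---|---|
| 0% | 44 vs 44 | 91.5% |
| 10% | 40 vs 44 | 90.1% |
| 25% | 33 vs 44 | 86.4% |
| 50% | 22 vs 44 | 74.9% |

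**The case against.** The staff-timing point is explicit in the text and hard to contest. The stronger objections are these.

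- **The endpoint is protected.** Cytology is scored centrally (14.6.1.1), the listed specimen identifiers omit the arm (14.3.1), the needle count is fixed, and a clinician performs the aspiration. This stands as a limit on the risk, and no bias is demonstrated. However, no visible passage says that this trial's cytopathologist is blinded; the blinded readings in Sections 1.3.2 and 1.3.3 belong to earlier studies.
- **A site can comply with every rule.** It could ask the question first, contact the woman after day 365, order by day 388 and hold the visit by day 395. That is possible, but only for late visits. A site with an earlier visit could ask the question before the offer, but the crossover procedure does not tell it to.
- **The question refers to the first 12 months,** so a woman told later can truthfully answer no. This is right for contact after day 365. It gives no protection to women crossing over whose visit falls on or before day 372.
- **One-sidedness rests on silence.** Section 7.3 does not forbid telling metformin women early, and only metformin tablets carry a printed code. But a metformin woman who identified her tablet was truly unblinded early, so her yes is correct. Any wrong exclusion affects sensitivity analyses, not the primary test.
- **Supply could lapse.** Assuming one 175-tablet bottle at registration and at months 3, 6 and 9, 700 tablets are dispensed, against 28 + 337 × 2 = 702 needed by day 365. This depends on the bottle assumption, and a visit early in the window leaves time to order. The delay is a real cost, but a manageable one.
- **Some pages are not shown,** including the consent form, Appendix VII and the treatment outline. A sequence might be stated there; if so, the visible sections still need to agree with it.

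**Conclusion.** The concern holds. Followed as written, Sections 4.0, 7.3 and 15.1.8 give site staff the arm before the month-12 RPFNA: at least 7 days before it wherever open-label drug is ordered, and for all 88 women planned at that time point. That placebo women who cross over learn their arm before the visit is an inference from the order of steps in 7.3.2, 6.9 and 15.1.8. It affects at most 44 women and conflicts with footnote 10 and Section 16.2.2.5 if the question is asked at the visit.

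No size or direction of bias can be derived from the documents, and none is claimed. The dates assume a 365-day year, and the power illustration assumes an exclusion share that the plan does not give. This is an avoidable weakness that should be fixed; it does not invalidate the trial. Section 16.2.2.5 argues that the results are safe from a single known patient incident, and that argument does not cover routine release to staff.

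**What to change.** Reconcile Sections 4.0, 6.9, 7.3 and 15.1.8 to one sequence:

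1. the arm-knowledge question is answered;
2. the month-12 RPFNA is collected;
3. the assignment is released to site staff and patient, crossover is offered, and re-registration is done.

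Align the timing of the month-12 open-label order with this sequence. The sponsor must settle how, since the present one-week lead cannot be kept unchanged if release follows the sample.

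For visits already completed, report by arm the dates of unblinding, of the arm-knowledge answer and of the RPFNA, together with the numbers of missing and unsatisfactory month-12 RPFNAs. This will show how often the order was reversed and whether attendance or sample adequacy differed between arms.

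The cost is protocol wording, one patient contact after the sample is taken, and a possible short delay in open-label supply.
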